## 6.3 Preliminary efficacy measures

eGFR (mL/min/1.73 m^2) is calculated from blood samples at screening and Weeks 0, 2, 8, 10 and 14 (if the study visit is conducted in person). Higher values generally indicate better kidney function. The calculation of eGFR could be found in Section 8.2.1.

UPCR (mg/mg) is calculated from urinary samples for proteinuria and creatinine at screening and Weeks 0, 2, 8, 10 and 14 (if the study visit is conducted in person). The preferred method for collection of urinary samples is through 24-hour urine collection, but first morning urine or spot urine is acceptable. The ratio of urine protein to urine creatinine (UPCR) is the secondary outcome measure of interest. Higher levels of UPCR indicate more significant kidney disease. In this pilot, proof-of-concept study, the normal range for UPCR is < 0.3 mg/mg for all ages.

## 6.4 Exploratory Outcome Measures

Intra-renal gene expression of TNF is derived from archived biopsy tissue of study participants or from the Nephrotic Syndrome Study Network (NEPTUNE) study data using the NEPTUNE study protocol and as published. [3] This parameter was only included for participants with biopsies within one year of consent in the TNF pilot study and is generated as a TNF activation score.

A TNF activation network was generated from expert curated interactions from NETPro annotations in the Genomatix Genome Analyzer database (Precigen Bioinformatics).[1] It was based on renal biopsy specimens available from more than 250 NEPTUNE participants with MCD and FSGS. From the database, causally downstream genes or proteins that increased expression from TNF exposure were used to generate a TNF activation score. Individual gene expression values were first Z-transformed. The TNF activation score for each participant was the average Z-score of the genes in their kidney RNA-seq profile and defines the intra-renal gene expression of TNF measure.

Urinary epidermal growth factor (uEGF, ng/ml) biomarker levels are assessed from spot urine specimens collected and normalized by urinary creatinine (mg/ml) at Screening, and Weeks 0, 2, 8, and 10. Higher levels of uEGF/uCr (ng/mg) indicate better kidney function.

The FSGS-MCD Patient Reported Outcome (PRO) score is still in development and scoring methods have not yet been finalized. The score will be derived from the FSGS-MCD PRO structured questionnaires completed by participants at in-person study visits at Weeks 0, 2, 8 and 10. The analyses of FSGS-MCD PRO scores will occur when the scoring methods have been developed and made available to the study investigators.

#### Assay Quality Methods:

Urinary MCP1, TIMP1, creatinine and EGF for all study participants and all time points for were assayed on the same plate to reduce batch effects.

## 7. Statistical Considerations

## 7.1 General Statistical and Analytical Plans

This is a pilot, proof-of-concept investigation to test the proposed biomarkers as indicators of target engagement. As such, no formal sample size calculations were performed, and analyses are primarily descriptive in nature. Our approach is to assess the biomarker change over time with TNF inhibition therapy within each patient and as a group. As the ELISA testing for this indication is new, the protocol uses an exploratory approach to assess individual and panel biomarker changes and correlations with clinical indicators of disease, including proteinuria, eGFR, and serum albumin.

This SAP document was finalized and approved prior to the database lock.

## 7.2 Analysis Dataset

All eligible participants who received at least one dose of adalimumab (as-treated population) are analyzed for primary, secondary, and exploratory endpoints.

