4.2.2 SECONDARY ENDPOINTS

- (1) Incidence of serious adverse events, adverse events and abnormal laboratory tests
- (2) Percent change of eGFR from baseline to week 10
- (3) Percent change in UPC from baseline to week 10
- (4) Proportion of participants achieving a nadir UPC less than 1.5 g/g and at least a 40% reduction from baseline at week 10.

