10.2 ANALYSIS DATASETS

All eligible participants who receive at least one dose of adalimumab (as-treated population) will be analyzed for primary, secondary and exploratory endpoints.

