#### 12.1 List of Tables

- Table 1. Subject Disposition Summary. All Subjects.
- Table 2. Reasons for Early Study Discontinuation. All Subjects.
- Table 3. Duration of Follow-Up Period. All Subjects.
- Table 4. Number of Enrolled Subjects by Site. All Subjects.
- Table 5. Proportion of Participants Receiving 1, 2, 3, 4 and 5 (all) Doses of Adalimumab. As-Treated Population.

- Table 6. Duration of Adherence to Study Medication Summary. As-Treated Population
- Table 7. Demographic and Baseline Characteristics. As-Treated Population.
- Table 8. Change in urinary MCP1/uCr levels from Baseline to Week 10. As-Treated Population.
- Table 9. Change in urinary TIMP1/uCr levels from Baseline to Week 10. As-Treated Population.
- Table 10.1. Treatment-Emergent Serious Adverse Event (SAE) Summary. As-Treated Population.
- Table 10.2. Treatment-Emergent Serious Adverse Event (SAE) by System Organ Class and by Severity. As-Treated Population.
- Table 10.3. Treatment-Emergent Serious Adverse Events (SAE) by System Organ Class and by Relatedness to Study Medication. As-Treated Population.
- Table 11.1. Non-Serious Treatment-Emergent Adverse Event (AE) Summary. As-Treated Population.
- Table 11.2. Non-Serious Treatment-Emergent Adverse Events (AE) by System Organ Class and by Severity. As-Treated Population.
- Table 11.3. Non-Serious Treatment-Emergent Adverse Events (AE) by System Organ Class and by Relatedness to Study Medication. As-Treated Population.
- Table 12.1. Treatment-Emergent Adverse Events Leading to Premature Discontinuation of Study Medication Summary. As-Treated Population.
- Table 12.2. Treatment-Emergent Adverse Events Leading to Premature Discontinuation of Study Medication by System Organ Class and by Severity. As-Treated Population.
- Table 12.3. Non-Serious Treatment-Emergent Adverse Events Leading to Premature Discontinuation of Study Medication by System Organ Class and by Relatedness to Study Medication. As-Treated Population.
- Table 13. Proportion of participants with temperature ≥38.5°C (indicating fever). As-Treated Population.
- Table 14. Proportion of participants with new or worsening edema (over all body locations and by each location) over the course of the 10-week intervention period compared to baseline. As-Treated Population.
- Table 15. Percent change in eGFR from baseline to week 10. As-Treated Population.
- Table 16. Percent change in UPCR from baseline to week 10. As-Treated Population.

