- Table 17. Proportion of participants achieving a nadir UPCR <1.5 g/g and at least a 40% reduction from baseline at week 10. As-Treated Population.
- Table 18.1. Proportion of Participants with Abnormal Laboratory Tests for ALT, AST, Total Bilirubin, Hemoglobin, Hematocrit, and Platelet Count Over the Course of the 10-Week Intervention Period. As-Treated Population.
- Table 18.2. Shift Table for Normal and Abnormal Laboratory Test Changes from Screening to Weeks 0, 2, 8, 10, and 14 in ALT, AST, Total Bilirubin, Hemoglobin, Hematocrit, and Platelet Count. As-Treated Population.
- Table 19. Correlations between TNF activation score and urinary MCP1/uCr and TIMP1/uCr biomarker levels at baseline. As-Treated Population with Kidney Biopsy Tissue Collected within 12 Months of Study Baseline.

- Table 20.1. Change from baseline to weeks 2, 4, and 8 in urinary MCP1/uCr. As-Treated Population.
- Table 20.2. Percent change from baseline to weeks 2, 4, 8, and 10 in urinary MCP1/uCr. As-Treated Population.
- Table 20.3. Urinary MCP1/uCr values at baseline and weeks 2, 4, 8, and 10. As-Treated Population.
- Table 21.1. Change from baseline to weeks 2, 4, and 8 in urinary TIMP1/uCr. As-Treated Population.
- Table 21.2. Percent change from baseline to weeks 2, 4, 8, and 10 in urinary TIMP1/uCr. As-Treated Population.
- Table 21.3. Urinary TIMP1/uCr values at baseline and weeks 2, 4, 8, and 10. As-Treated Population.
- Table 22. Change in uEGF/uCr levels from baseline to weeks 2, 4, 8, and 10. As-Treated Population.
- Table 23. Correlation coefficient between uEGF/uCr at baseline with changes and percent changes in urinary MCP1/uCr and urinary TIMP1/uCr biomarker levels and in eGFR and UPCR values at week 10. As-Treated Population.
- Table 24. Changes in FSGS-MCD Patient Reported Outcome (PRO) score from baseline to weeks 2, 4, 8 and 10. As-Treated Population.

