## 12.2 List of Listings

- Listing 1. Dosing Data. As-Treated Population.
- Listing 2. Reasons for Permanent Discontinuation of Study medication. As-Treated Population.
- Listing 3. Serious Adverse Events (SAEs). As-Treated Population.
- Listing 4. Non-Serious Adverse Events (AEs). As-Treated Population.
- Listing 5. Deaths. As-Treated Population.
- Listing 6. Adverse Events Leading to Premature Discontinuation of Study Medication.
   As-Treated Population.
- Listing 7. Protocol Deviations. All Subjects.

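### The only analysis set requires eligibility as well as a dose, so read literally the safety outputs could omit a participant who was given adalimumab without qualifying for it

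*SAP*

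**What the plan says.** SAP 7.2 gives one population with two conditions, eligibility and a dose, and applies it at all three endpoint levels: "All eligible participants who received at least one dose of adalimumab (as-treated population) are analyzed for primary, secondary, and exploratory endpoints". Protocol 10.2 has the same two conditions: "All eligible participants who receive at least one dose of adalimumab (as-treated population) will be analyzed for primary, secondary and exploratory endpoints". Neither document defines a separate safety population. SAP section 10, which lists departures from the protocol, does not mention the analysis set.

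Safety falls under this rule because it is the first secondary endpoint in Protocol 4.2.2: "Incidence of serious adverse events, adverse events and abnormal laboratory tests". The output list in SAP section 12 follows through:

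- The adverse event, fever and edema tables (10.1 to 14) all carry the label, for example "Table 10.1. Treatment-Emergent Serious Adverse Event (SAE) Summary. As-Treated Population".
- Laboratory Tables 18.1 and 18.2 carry it too; the title of the first ends "Over the Course of the 10-Week Intervention Period. As-Treated Population".
- So do Listings 3 to 6, among them "Listing 5. Deaths. As-Treated Population".

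The outputs on All Subjects are Tables 1 to 4, Listing 7 and Figure 1. They cover disposition, follow-up, site, deviations and participant flow. SAP 7.2 does not say what *eligible* means or at what moment it is fixed.

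**The concern.** A safety summary should cover everyone exposed, because harm depends on receiving the drug and not on having met the entry criteria. With an eligibility condition in the only population, data collection follows exposure while reporting follows eligibility. The two differ exactly when someone is dosed who did not qualify.

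That participant matters for safety. Protocol 2.3.1 says the entry criteria were chosen partly to keep out people more prone to treatment-related toxicity. An exposed participant who failed a criterion may therefore be among the more informative for harm. In a trial of at most 8 treated patients, each one is also a large share of the denominator.

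**Working it through.** The plan states no figure on this point, so there is nothing to reproduce. The check sets the sections side by side and then sizes one exclusion.

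**1. Who is recorded and who is reported**

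| Step | Place | Condition |
|---|---|---|
| Recording of adverse events | Protocol 8 | exposure to adalimumab |
| Recording of adverse events | SAP 6.2.1 | administration of adalimumab |
| Adverse event and laboratory tables | SAP 7.2 with 12.1 | exposure **and** eligibility |
| Serious event, adverse event, death and discontinuation listings | SAP 7.2 with 12.2 | exposure **and** eligibility |

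The recording rules carry no eligibility condition. The reporting rule does.

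**2. When eligibility is decided**

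- Protocol 7.2.1: a patient meeting all criteria is declared eligible and then invited to the baseline visit; anyone else is a screen failure and leaves the study.
- Protocol 5.3: it is eligible patients who start the intervention.
- SAP section 10, item 1: the screening protocol settled who was eligible for the drug.

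All three place the decision before the first dose. On that meaning, everyone properly dosed is eligible and the set equals everyone dosed.

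**3. What that meaning leaves uncovered**

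- A participant dosed in error, who never met the criteria.
- A participant whose biopsy report goes to central review to confirm the pathology (Protocol 7.1 and 7.2.1). No text says this review must finish before dosing.

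For these two cases the literal wording of SAP 7.2 and Protocol 10.2 removes the participant from the safety tables and listings, and no other text puts them back.

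**4. Size of one exclusion (illustration)**

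Inputs: maximum treated N = 8 and minimum evaluable 6 (Protocol 4.1). Assumption: one dosed participant is classed as ineligible.

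Share of exposure lost = 1/N:
- N = 8: 1/8 = 12.5%
- N = 7: 1/7 = 14.3%
- N = 6: 1/6 = 16.7%

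Extreme case, assuming also that this participant has the only serious event. Limits are exact (Clopper-Pearson) 95%; the upper limit for 0 of m is 1 − 0.025^(1/m).

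| N dosed | Set by dose alone | Set as written |
|---|---|---|
| 8 | 1/8 = 12.5% (0.3% to 52.7%) | 0/7 = 0% (upper 41.0%) |
| 7 | 1/7 = 14.3% (0.4% to 57.9%) | 0/6 = 0% (upper 45.9%) |
| 6 | 1/6 = 16.7% (0.4% to 64.1%) | 0/5 = 0% (upper 52.2%) |

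**5. How likely the extreme case is**

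Protocol Table 3 reports infection with hospitalization in 5 of 17 earlier patients (29.4%, printed as 30%). If that rate applied here:

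- Expected number with such an event among 8: 8 × 5/17 = 2.4.
- Chance of at least one: 1 − (12/17)^8 = 93.8% with 8 patients and 1 − (12/17)^7 = 91.3% with 7.
- Given that one participant is excluded, the chance that this one has the only such event: (5/17) × (12/17)^7 = 2.6%.

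So the likelier effect of an exclusion is a wrong numerator and denominator, not a clean record. The 5/17 is itself only a guide: it comes from multi-drug resistant patients, and Protocol 2.3.2 describes that earlier experience over 16 weeks, against 8 weeks of treatment here.

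**The case against.** The strongest reply is that *eligible* in these documents is the screening verdict, reached before the drug is given. Protocol 5.3 and 7.2.1 and SAP section 10 all use it that way, and the name as-treated points to everyone dosed. On that reading the word excludes nobody who was properly dosed. This largely stands, and it is why the set will usually be right. It does not cover a participant dosed in error, or one whose central biopsy review is still open at dosing, and the word remains in both definitions.

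A second reply is that nothing would be lost from oversight. This also stands. Protocol 8.4.2 sends serious events to the coordinating center, the principal investigator and the IRB within 24 hours. Protocol 8.6 gives the DSMB serious and treatment-emergent events. The participant would appear in the All Subjects disposition tables, the CONSORT figure and the deviation listing. A reader might infer that events in such a participant would disappear from the trial altogether; the documents do not support that. What is lost is their place in the reported safety tables and listings.

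A reader might also infer that the wording lets someone drop a dosed patient after seeing the outcome, and that inconsistent entry criteria make this likely. The documents do not support that either. No section provides for judging eligibility again after dosing or for removing a dosed patient from analysis. The Protocol summary does apply the eGFR and proteinuria limits at enrollment, but Protocol 5.1 and SAP 5.2.1 both apply them at screening. The differing statements of the biomarker criterion concern who is admitted and are a separate matter.

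**Conclusion.** The point holds as a conditional gap in the definition. SAP 7.2 and Protocol 10.2 attach an eligibility condition to the only population, and every adverse event, laboratory and death output listed in SAP section 12 uses it. If a participant is dosed in error or found ineligible after dosing, the literal rule leaves that exposed person out of the safety summary, against the exposure-based recording in Protocol 8 and SAP 6.2.1.

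The size is 12.5% of the exposure per such participant if 8 are treated (16.7% if 6 are). This assumes that a case occurs, and the documents report none. The change from 1/8 to 0/7 is an extreme illustration. A reader might pair it with the 5/17 history to conclude that the safety summary is likely to show no serious events; at that rate several patients would be expected to have one, so the pairing does not work.

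Whether ineligible participants belong in the biomarker analysis is a more open question, and a restriction there is easier to defend. The firm conclusion is about safety only. The correction is worth making because it costs almost nothing and, if all dosed participants were intended, changes no result.

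**What to change.** 1. Add a safety population to SAP 7.2 and Protocol 10.2: everyone given one or more adalimumab doses, whether or not they met the entry criteria.
2. Use it for Tables 10.1 to 14, Tables 18.1 and 18.2, and Listings 3 to 6. The laboratory plots (Figures 6.1 to 6.6) carry the same label and should match.
3. For the biomarker endpoints, either use the same set or keep *eligible* and state that it means the decision made at screening before the first dose, not revised afterwards.
4. Report eligibility deviations in Listing 7, which already covers All Subjects, and note the change in SAP section 10.

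Simply deleting *eligible* from the single definition would also repair the safety outputs, but it would settle the biomarker question without discussion. A separate safety set avoids that. The cost is one extra population label; no new data or analysis is needed, and if nobody ineligible was dosed the two sets are identical.

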## 7.3 Covariates and Subgroups

No adjustment for covariates is included in the analyses of the primary biomarker endpoints because of the limited sample size of this pilot, proof-of-concept study. No subgroup analyses are planned.

## 7.4 Missing Data

For the primary analysis of the primary endpoints, we will impute week 10 biomarker values using the week 8 biomarkers values, when needed. The remainder of our analyses uses a complete case approach (i.e., analyzing the observed values with no imputation of missing values). This method is valid under the missing completely at random assumption. We will assess the suitability of this assumption based on the extent and patterns of missingness, as well as clinical judgement.

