2.3.2 POTENTIAL BENEFITS

In previous studies 4 of 17 (24%) of unselected patients with multi-drug resistant FSGS experienced a 50% reduction in proteinuria and preservation of eGFR with the use of TNF-inhibitor with monoclonal antibody therapy over a 16 week period⁵.

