5.4 PARTICIPANT WITHDRAWAL OR TERMINATION

5.4.1 Reasons for Withdrawal or Termination

Patients participating in this study may withdraw or be terminated for the following anticipated reasons.

- Ongoing participation in this research study is voluntary and patients may leave at any time without an identified cause or the need for explanation.
- Patients experiencing any clinical adverse event (AE), laboratory abnormality, or other medical condition or situation such that continued participation in the study would not be in the best interest of the participant (as determined by the patient and/or study physician).
- Pregnancy and/or breast feeding
- Absolute contraindications to continued therapy with Humira.

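### The complete-case rule in SAP 7.4 removes treated participants without a week 10 UPCR from the responder proportion, which conflicts with SAP 7.2 and Table 17 and can overstate the rate

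*SAP*

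**What the plan says.** SAP 7.4 contains one imputation rule, and it covers the biomarkers only: "For the primary analysis of the primary endpoints, we will impute week 10 biomarker values using the week 8 biomarkers values, when needed". Everything else comes under the next sentence: "The remainder of our analyses uses a complete case approach (i.e., analyzing the observed values with no imputation of missing values". The section gives the condition for this, "This method is valid under the missing completely at random assumption", and adds a check: "We will assess the suitability of this assumption based on the extent and patterns of missingness, as well as clinical judgement". It names no analysis to use if the check fails.

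The UPCR responder proportion is item 7 of the secondary endpoints in SAP 4.2, so the complete-case rule applies to it. SAP 9.2 adds only that it is summarised descriptively. Protocol 7.2.4 leaves missing data to suitable methods without naming one.

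Two other places in the SAP describe a different denominator. SAP 7.2 states: "All eligible participants who received at least one dose of adalimumab (as-treated population) are analyzed for primary, secondary, and exploratory endpoints". The title of Table 17 in SAP 12.1 reads: "Proportion of participants achieving a nadir UPCR <1.5 g/g and at least a 40% reduction from baseline at week 10. As-Treated Population".

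The documents also try to keep week 10 data complete. Protocol 5.4.2 and 7.2.4 ask participants who leave early, whatever the reason, to come back for the week 10 assessments. SAP 5.1 keeps participants in follow-up after they stop drug unless they withdraw consent.

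**The concern.** A responder proportion needs a fixed denominator. Under SAP 7.2 and the label of Table 17 it is everyone dosed. Under SAP 7.4 it is everyone dosed who has a week 10 UPCR. Two programmers could each follow the SAP and report different rates from the same data.

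The complete-case version also has a likely direction of error. Protocol 5.4.1 lists among the anticipated reasons for withdrawal: "Patients experiencing any clinical adverse event (AE), laboratory abnormality, or other medical condition or situation such that continued participation" is judged not to serve the participant. A participant who leaves for such a reason and does not return at week 10 is hard to regard as missing completely at random. If that participant would not have responded, removal from the denominator raises the reported rate.

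The point estimate is what will be used. SAP 7.6 bases inference and decisions mainly on the size of effects, and the endpoint rationale in SAP 4.3 says urinary protein is measured to give estimates for later trials.

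**Working it through.** **Plan's own figure.** Neither document gives an expected response rate or a precision for this endpoint, so there is nothing to reproduce. The only computed figure, a detectable effect size for the biomarkers, is not an input here.

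**Inputs.**
- *N*, number treated: at most 8 (protocol 4.1 and 5.3). SAP 9.5 works with 7, so both are shown.
- *m*, treated participants with no week 10 UPCR: not given in the documents. Assumed to be 1 or 2.
- *r*, observed responders: not given. Assumed to be 2, with 3 as a variant.
- *k*, the number of the *m* who would have responded: unknown, from 0 to *m*.

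**Formulas.**
- Complete case (SAP 7.4): r/(N − m).
- All treated, missing counted as non-response: r/N.
- Best case, all missing counted as response: (r + m)/N.

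| N | m | r | Complete case | Missing = non-response | Difference | Best case |
|---|---|---|---|---|---|---|
| 8 | 1 | 2 | 2/7 = 28.6% | 2/8 = 25.0% | 3.6 points | 3/8 = 37.5% |
| 8 | 2 | 2 | 2/6 = 33.3% | 2/8 = 25.0% | 8.3 points | 4/8 = 50.0% |
| 8 | 2 | 3 | 3/6 = 50.0% | 3/8 = 37.5% | 12.5 points | 5/8 = 62.5% |
| 7 | 1 | 2 | 2/6 = 33.3% | 2/7 = 28.6% | 4.8 points | 3/7 = 42.9% |

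**When complete case overstates.** The rate among all treated, had everyone been observed, is (r + k)/N. Complete case exceeds it when rN > (r + k)(N − m), which reduces to k/m < r/(N − m). In words, the missing participants would have responded less often than the observed ones. For N = 8, m = 2, r = 2:
- k = 0: 33.3% against 25.0%, overstated by 8.3 points.
- k = 1: 33.3% against 3/8 = 37.5%, understated by 4.2 points.
- k = 2: 33.3% against 50.0%, understated by 16.7 points.

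If r = 0, both the complete-case and the non-response figures are 0%. If values are missing completely at random, no bias is expected.

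**Scale against sampling error.** Exact 95% intervals are about 4% to 78% for 2/6 and 3% to 65% for 2/8.

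**The case against.** The strongest reply is that the plan already limits the problem. Stopping drug does not remove anyone, because a week 10 return is requested and follow-up continues unless consent is withdrawn. A reader might infer from the complete-case sentence that withdrawal for worsening or toxicity in itself raises the response rate. The documents do not support that: a participant who stops early and attends week 10 stays in the denominator. What remains is that a return is requested and cannot be guaranteed. Those still missing are the ones who did not come back, withdrew consent or died.

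A reader might also take the goal in protocol 5.3, 8 starting and at least 6 completing, as an allowance for two missing values and so infer a fixed inflation of 8/6 = 1.33. That goal concerns completing the five doses, not UPCR at week 10. The factor also holds only if both missing participants would have been non-responders.

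A third tempting step is to compare the rate with protocol 2.3.2: "In previous studies 4 of 17 (24%) of unselected patients with multi-drug resistant FSGS experienced a 50% reduction in proteinuria". That outcome also required preserved eGFR, ran over 16 weeks and came from unselected multi-drug resistant FSGS. This endpoint is UPCR below 1.5 g/g with a 40% reduction at week 10, in biomarker-selected FSGS or TR-MCD. Neither document makes the earlier figure a comparator, so it cannot serve as one under either denominator.

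On the check of the assumption, the SAP promises clinical judgement and no formal test. With so few participants, and with reasons for early discontinuation tabulated in Table 2, case-by-case judgement is possible. That is fair, but the SAP does not say what happens to the estimate if the judgement is unfavourable.

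Finally, the endpoint is secondary and descriptive, no test or error rate is affected, and the intervals far exceed the shift. The CONSORT diagram and the individual UPCR plots (Figures 5.1 to 5.3) would let a careful reader recompute the rate. This limits the importance of the point. It does not remove the conflict over the denominator.

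**Conclusion.** The point holds in a limited form. SAP 7.4 drops treated participants with no week 10 UPCR from a proportion that SAP 7.2 and Table 17 assign to everyone treated. The rate is overstated if those participants would have responded less often than the rest, which requires at least one observed responder. Protocol 5.4.1 makes that plausible but does not establish it.

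With 8 treated and 2 responders, and with the missing participants as non-responders, the excess is 3.6 points for one missing value and 8.3 points for two. Both the number missing and the number of responders are assumptions. If there is no missing week 10 UPCR, the two denominators agree and nothing changes. The primary biomarker analysis is not affected. This should be corrected because the estimate is meant to inform later trials, but it does not threaten the trial's main conclusion.

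**What to change.** In SAP 7.4, exempt the UPCR responder endpoint from the complete-case sentence. In SAP 9.2 and Table 17, state that:
- the denominator is every participant who received at least one dose;
- a participant without a week 10 UPCR counts as a non-responder;
- the observed-case proportion and the best-case bound, (r + m)/N, appear beside the main figure as supportive results, with the number missing.

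The cost is a sentence or two in the SAP and extra rows in Table 17, with no new data. The main figure becomes conservative and may be slightly lower. A participant who was responding at week 8 but whose week 10 sample was lost would count as a failure, which is why the observed-case and best-case figures should be shown with it. The term nadir is undefined and would still need its own definition. That does not alter the present point, because the 40% reduction is tied to week 10.
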